Rationale: We wish to focus only on adult smokers since adolescent smokers present unique issues that merit separate consideration.

- Smoking status of current smoker in structured field of EHR

Rationale: Using the EHR to identify and reach out to smokers leverages smoking status documentation promoted by federal Meaningful Use standards and makes the intervention potentially scalable to any healthcare system with smoking status documented in their EHR.

- Language listed as English in EHR

Rationale: We do not have the resources to develop intervention materials in languages other than English at this time.

- PCP within Partners Healthcare system and MGH medical record number

Rationale: This intervention is designed to target patients engaged in primary care. Patients undergo chart review by PI as part of eligibility screening for possible contraindications to NRT and this is possible only with Partners primary care patients. Subjects require an MGH MRN because some patients will be randomized to NRT prescribed through MGH Epic and sent through the MGH pharmacy. Subjects who report cessation will also be asked to come to MGH for an exhaled carbon monoxide assessment to confirm tobacco abstinence at the end of the 12 week study.

- PCP visit in the past 2 years

Rationale: We want to include patients who are actively engaged in primary care.

- Mobile telephone number listed in EHR

Rationale: We need an active mobile number for the patient to receive text messages.

- Potential TSS referred subjects who have been recently hospitalized for a heart attack or chest pain may participate in the study with approval from their primary care physician.

Rationale: Smokers who have been hospitalized for a recent heart attack or chest pain may likely use nicotine replacement therapy during their admittance. If there are no contradictions with other medications and their primary care physician approves of nicotine replacement therapy usage then it will be safe to enroll them.

Individuals meeting **any** of the following criteria will be excluded from the study:

- Not a current daily smoker defined as not having smoked ≥ 100 cigarettes in lifetime or not having smoked in the last 30 days

Rationale: EHR smoking status of current smoking will be verified by self-report using the CDC's definition of current smoking. We exclude non-daily smokers because our primary outcome of self-reported quit attempts has not been well-studied among non-daily smokers.

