- Unwilling or unable to receive and participate with a text message program for up to 12 weeks.

Rationale: We will not require that users have unlimited text messaging in their telephone plan, rather we will provide payment at baseline that should offset any costs incurred by sending or receiving text messages for the intervention.

- Pregnant, planning to become pregnant in the next 3 months, or breastfeeding.

Rationale: The use of nicotine replacement therapy in pregnant smokers requires close monitoring, and the treatment of pregnant smokers more generally presents unique challenges that go beyond the scope of the present study.

Past 30 day use of nicotine replacement therapy, bupropion, or varenicline. For TTS referred patients: Use of nicotine replacement therapy in the 30 days prior to hospital admission

Rationale: In order to better isolate treatment effects for the proposed interventions, we wish to focus on individuals who are not currently using medications to try to quit smoking.

- Past 30-day use of Massachusetts state quitline, QuitWorks or SmokefreeTXT programs. For TTS referred patients: Use of Massachusetts state quitline, QuitWorks or SmokefreeTXT programs in the 30 days prior to hospital admission.

Rationale: In order to better isolate treatment effects for the proposed interventions, we wish to focus on individuals who are not currently receiving behavioral interventions for smoking cessation.

- Prior serious adverse reaction to the nicotine patch or lozenge defined as any reaction that was life-threatening, required hospitalization, or other clinical evaluation

Rationale: Nicotine replacement therapy is a component of both arms of the study.

- Weight < 100 pounds

Rationale: Nicotine replacement therapy is a component of both arms of the study and requires clinical consultation for individuals under 100 pounds.

- New or increasing chest pain or heart attack in the past 30 days.

Rationale: Although likely safer than smoking cigarettes, use of nicotine replacement therapy might pose a risk to individuals with unstable cardiac conditions.

- Ever been told by a doctor that patient has an irregularly fast, abnormal heartbeat

Rationale: Although likely safer than smoking cigarettes, use of nicotine replacement therapy might pose a risk to individuals with unstable cardiac conditions.

- Ever been told by a doctor that patient has dementia, psychosis or schizoaffective disorder.

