Rationale: This intervention is primarily conducted by telephone and we do not believe it is appropriate for patients with these conditions which may affect cognition and thought processes.

For patients who are eligible by these criteria will be invited to participate in the study and complete verbal informed consent. Following verbal informed consent, the PI will review their medical chart for contraindications to nicotine replacement therapy and diagnoses of dementia, psychosis, schizophrenia, Alzheimer's disease, delirium, or schizoaffective disorders. Any subjects with contraindications to NRT or these diagnoses will be notified that, following

review of their medical record they are not eligible and they will be provided with information about the MGH tobacco cessation counseling services, the state quitline, and National Cancer Institute's smokefreeTXT. Subjects without contraindications will be randomized.

a. Source of subjects and recruitment methods

Smokers will be recruited through four methods. The primary method is through proactive outreach to individuals who receive primary care at MGH and are identified in the health record as smokers. We will first ask PCPs to review their patients meeting inclusion criteria per electronic health records and designate any patients who they do not want us to contact for the study. We will then send letters, signed by the study PI and signed with secretarial notation by the PCP, to patients meeting the inclusion criteria to introduce the study. The letter will notify patients that they will be receiving a call about the study at their home or mobile telephone number as listed in their clinic registration. Patients will be provided with a number which they can call if they do not want to receive the telephone call or if they want to update their mobile telephone number. The letter will also include a study fact sheet. One week after the letter, participants who do not opt-out will then be contacted by telephone by a study RC to enroll and consent the patient to participate in the randomized trial. The RC will attempt to contact the patient up to 5 times (either 3 times leaving messages or 5 times if unable to leave messages) at the home or mobile phone number listed in their Epic registration data. At the recruitment phone call, the RC will assess patients for exclusion criteria.

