This will be a 4 arm randomized controlled trial among 206 smokers who are patients at Massachusetts General Hospital and who receive primary care from a Partners primary care provider. Patients will be proactively recruited from MGH primary care practices. Patients will also be recruited from online advertisements on the Partners Clinical Trials website, from among MGH primary care patients who consent to participate in Research Offers Direct to You, and by referral from the MGH inpatient Tobacco Treatment Service counselors. We will recruit both smokers who are ready to quit smoking in the next 30 days and those who are not planning to quit in the next 30 days. The text message program is tailored to readiness to quit. For those ready to quit in the next 30 days, they will be sent messages based on the SmokeFreeTXT content. For those not ready to quit, we have developed content including motivational advice and tips to try a practice quit attempt for a few hours or days.⁵³ The text message program will also include medication adherence support text messages based on the Information-Motivation-Behavioral Skills model of adherence.⁵⁴ Combination NRT is first-line therapy which is more effective than nicotine patch alone and will be offered to daily smokers, dosed per package instructions.²¹ Smokers who are not ready to quit and who are randomized to one of the two nicotine medication arms will be offered one box of lozenges to try in a practice quit attempt.⁵³

The RC will not be blinded to treatment assignment because he/she will register subjects randomized to the text messaging arms in the text messaging program during the enrollment telephone call to verify receipt of an enrollment confirmation text message ("Hi [First name] Welcome to getReady2Quit (R2Q). Your messages and ratings will start soon. Reply STOP to quit, HELP for info. Msg&DataRatesMayApply"). Randomization will be done by a computer generated random sequence.

b. Procedures for obtaining informed consent (including timing of consent process)

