Permission from primary care providers (PCP) or MGH inpatient Tobacco Treatment Service counselors will be obtained before making any patient contact unless the patient participates in 'Research Opportunities Direct to You' or proactively contacts the study in response to online advertisements. For PCP approval, providers will be given a list of smokers identified for the study and asked to identify any individuals who should not be (see "PCP Permission Email") contacted. Patients whose PCP's consider them to be inappropriate or ineligible for the study will be excluded from participation regardless of RODY status or self-selection. MGH inpatient

Tobacco Treatment Service counselors will introduce the study to interested patients they deem appropriate during a counseling visit. Patients who are considered eligible will be sent a letter from their PCP and a letter from the study PI if PCP approved, from the PI only if RODY consented, or the PI only if TTS counselor referred. The letter notifies patients that they will be receiving a telephone call inviting them to participate at the mobile telephone number listed in their clinic registration. The letters will include a copy of a study information fact sheet with informed consent content.

Patients sent study introduction letters-will be provided with a number which they can call in the letter if they do not want to receive the telephone call or if they want to update their mobile telephone number. Approximately one week after the letter, smokers who do not opt out will be contacted by telephone by a study RC who will screen for eligibility.

Patients who proactively contact the study will be sent more information on the study via mail and email. Patients with MGH MRNs and a Partners PCP will be considered eligible to proceed.

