Rationale: In order to test the effect of text messaging on medication adherence, we need to have treatment groups receiving medication and medication plus text messaging. To deliver medication, mailed NRT, like text messaging, reaches patients outside of the busy office visit. Mailed NRT alone has also been shown to increase cessation⁵⁵ and may itself be an effective intervention compared to standard care.

3. Text messaging (TM): Brief advice + 12 week personalized, tailored text messaging program.

Rationale: Text messaging shows promise as an intervention to help smokers to quit.^{8,56} However, it has not been well tested among primary care patients. Text messaging may connect those primary care smokers who do not access currently available treatment services like telephone counseling or prescribed medication with assistance outside of the clinic office.

4. Text messaging and nicotine replacement therapy (TM+NRT): Brief advice + 12 week personalized, tailored text messaging program + 2 weeks of nicotine patches and/or lozenges mailed to subject.

Rationale: As above, in order to test the effect of text messaging on medication adherence, we need to have treatment groups receiving medication and medication plus text messaging. Text messaging has been shown to increase medication adherence in other conditions³⁴⁻³⁷ and medication adherence is suboptimal among users of smoking cessation medications.^{38,39,41} Integrating text messaging within healthcare systems offers opportunities to coordinate with pharmacotherapy and this 4 group design allows us to test the effect of text messaging alone on smoking outcomes and the effect of text messaging on NRT use.

We will use stratified block randomization. We will stratify by practice and readiness to quit in the next 30 days. We will use variable block sizes. Subjects will be randomized 1:1:1:1.

After verbal consent and chart review by the PCP. Randomized enrollees will be asked to complete a baseline telephone survey. After completion of the baseline survey, participants will be mailed a \$20 gift card.

Following the telephone survey, smokers randomized to the text messaging arms (TM and TM+NRT) will have their mobile numbers, and first names entered into the MobileCommons web-based platform. The program will be tailored to readiness to quit and user-entered quit date and personalized with individual's first name.

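### The only live test that a phone receives texts comes after randomization and only in the two text arms, although ability to receive texts is an entry condition for everyone

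*Combined protocol and SAP*

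**What the plan says.** **Before randomization, all arms.** Section III requires a "Mobile telephone number listed in EHR", and gives the reason: "We need an active mobile number for the patient to receive text messages". The exclusion list in the same section removes anyone "Unwilling or unable to receive and participate with a text message program for up to 12 weeks". Section III.a places that screen early: "At the recruitment phone call, the RC will assess patients for exclusion criteria". Under sections III.a and IV.b, the introduction letter gives patients a number to call "if they want to update their mobile telephone number".

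**After randomization, text arms only.** Section IV.a explains that the coordinator is unblinded because he or she registers patients assigned to the text arms in the program "during the enrollment telephone call to verify receipt of an enrollment confirmation text message". Section IV.c agrees on who is registered: "smokers randomized to the text messaging arms (TM and TM+NRT) will have their mobile numbers, and first names entered into the MobileCommons web-based platform".

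**Later.** Section V.d asks about receipt of texts at weeks 1, 2 and 6, with no restriction by arm. Section VI makes the primary analysis intention-to-treat. It pools TM and TM+NRT against BA and NRT unless an interaction is found, in which case TM is compared with BA.

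No test text before allocation is described, and no rule covers a confirmation that fails.

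**The concern.** The plan treats ability to receive texts as a condition of entry and thinks it worth checking live. It then places the check where it can no longer decide entry. A patient who fails it appears to meet an exclusion criterion but has already been assigned. A patient in BA or NRT with the same phone is never identified, because no text is sent there.

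If the patient is kept, as intention-to-treat implies, a text-arm patient receives no texts and the contrast moves toward the null. If an unblinded coordinator withdrew or replaced the patient, the loss would fall on the text arms alone. The protocol does not call for removal, but it has no sentence specific to this situation. Testing everyone before allocation largely avoids both problems.

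**Working it through.** **Inputs from the documents.** 50 patients per group, 25% loss to follow-up, relative risk 1.8, stated power 81% (section VI, Sample size). Alpha 0.05 is stated there for Hypotheses 4 and 5 only; I take it as two-sided throughout.

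**Assumed, because not given.** The control quit-attempt rate p0, and the share u of text-arm phones that stay unreachable. I also assume that unreachable patients quit at the control rate and that 1.8 applies to reachable phones.

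**Formulas.** Unreachable phones give p1 = p0 × [1 + 0.8 × (1 − u)], so the diluted relative risk is 1 + 0.8 × (1 − u). With n per side, d = p1 − p0 and p̄ the mean of the two rates,

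power = Φ{ [d − 1.96 √(2p̄(1 − p̄)/n)] / √([p0(1 − p0) + p1(1 − p1)]/n) }.

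**The plan's own 81%.** It cannot be reproduced uniquely without p0, but it is attainable in two ways:
- TM versus BA, n = 50 × 0.75 = 37.5 per side: 40% versus 72% gives 81.0%.
- Pooled text versus no text, n = 100 × 0.75 = 75 per side: 28.1% versus 50.5% gives 81.0%.

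The companion figures fit 75 per side: Hypothesis 3 gives 81.3% (stated 80%), Hypothesis 4 gives 68.8% (68%) and Hypothesis 5 gives 74.7% (75%).

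**Worked example.** Pooled contrast, p0 = 0.40, u = 0.05: p1 = 0.40 × (1 + 0.8 × 0.95) = 0.704 and d = 0.304. The two standard errors are 0.0812 and 0.0773. Then (0.304 − 1.96 × 0.0812)/0.0773 = 1.87, and power is 96.9%.

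| Unreachable share u | Diluted RR | Pooled, 75 v 75, p0 = 40% | Pooled, 75 v 75, p0 = 28.1% | TM v BA, 37.5 v 37.5, p0 = 40% |
|---|---|---|---|---|
| 0% | 1.80 | 98.2% | 81.0% | 81.0% |
| 2% | 1.78 | 97.8% | 79.4% | 79.2% |
| 5% | 1.76 | 96.9% | 77.0% | 76.5% |
| 10% | 1.72 | 95.1% | 72.6% | 71.5% |

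**Loss on the first-line pooled contrast.** At u = 5%: 98.2 − 96.9 = 1.3 points, or 81.0 − 77.0 = 4.0 points. At u = 10%: 98.2 − 95.1 = 3.1 points, or 81.0 − 72.6 = 8.4 points. On the fallback contrast the losses are 4.5 and 9.5 points.

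**The case against.** The case on the other side is substantial.

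- **All arms are screened.** A reader might infer that the control arms have no check at all. They do: the listed number and the exclusion questions apply to everyone before allocation, and the letter invites corrections. On the recruitment call the coordinator also discusses message costs and payments. The baseline interview asks about daily text volume, carrier, phone type and plan. Only the live test is one-sided. These screens limit the problem but do not test delivery. Section III.a allows the recruitment call to go to a home number, while section IV.b mentions only the mobile, so answering the call does not settle it.
- **The check helps.** It is made during the call, so a wrong number can be corrected at once. Only phones that stay unreachable dilute the effect.
- **No bias is shown.** A reader might infer that the randomized comparison is broken. That would need failures to be removed or replaced. The documents do not say they are, and the primary analysis is intention-to-treat. Unidentified unreachable phones in BA and NRT do no harm, since those arms receive no program texts and randomization balances such patients in expectation.
- **Non-delivery may belong to the effect.** The pilot studies an offer of text outreach in primary care, and receipt is asked about later. If the meta-analyses behind the 1.8 already include non-delivery, the losses above are overstated.

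All four points stand as limits on size. None explains why the live test should follow allocation when it could precede it.

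**Conclusion.** The point holds as a minor design improvement. An eligibility condition common to all arms gets its only live test after allocation, in two arms of four, with no stated handling of a failure.

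The dilution is conditional and modest: about 1 to 4 power points at an assumed 5% unreachable and about 3 to 8 at 10%, on the pooled contrast with a control rate between 40% and 28%. It rests on a failure share and a control rate that the documents do not give, and the figures are upper bounds if 1.8 already allows for non-delivery. The larger drop in the table's last column should not be read as the trial's expected loss, because TM versus BA is the primary comparison only if an interaction is found. Nothing here shows an error in the planned analysis.

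**What to change.** After consent and before randomization, send one neutral test text to every patient. Confirm receipt on the call, or correct the number and try again. If receipt still fails, apply the exclusion already in section III. This works whichever order is intended for the baseline survey and randomization, on which sections IV.b and IV.c differ.

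Keep the welcome text in TM and TM+NRT. A test text from a study phone shows that the number accepts texts, not that the messaging platform reaches it, so the welcome text still has a use. Add one sentence: a failed welcome text is recorded and followed up, and nobody is removed from the intention-to-treat analysis because of it.

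The cost is one text per consented patient. A few patients will be screened out, and patients later assigned to BA or NRT will have received one message without content.

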Eligible subjects who are interested in enrolling will be offered a call back the next day to allow 24 hours to consider enrollment. For those that decline this additional time or at the time of the call the next day, the study RC will complete verbal informed consent (see "Consenting call script"). For those subjects who complete verbal informed consent but report they no longer have a copy of the study information fact sheet that was mailed with the Opt Out Letter, a new copy of the study information fact sheet will be mailed. Following verbal informed consent, the PI will screen the medical chart of consented subjects for NRT contraindications or diagnoses in the exclusion criteria (dementia, psychoses, and schizoaffective disorder). Subjects without contraindications will undergo baseline survey and then be randomized.

Rationale: There is a precedent for mailing nicotine replacement therapy to smokers after telephone screening for contraindications to the medication. The precedent is based on the methods used by the Massachusetts State quitline, we include screening questions used by the quitline in our eligibility screener. Our approach to screening for medical contraindications is more robust than that used by the quitline in that the PI-[name] also conduct a chart review for medical contraindications or psychiatric diagnoses that may make a remotely conducted study inappropriate. Finally, Partners has approved at least two other randomized controlled trials that mailed nicotine replacement therapy following verbal consent and telephone screening (protocol 2009-P-001137/3 and 2011-P-000644/1).

c. Treatment assignment, and randomization

Those who consent and enroll will be randomly assigned to one of 4 groups:

1. Brief advice (BA): Brief advice to quit smoking

Rationale: All subjects will receive brief advice from a trained RC. All primary care subjects also have access to guideline-concordant tobacco treatment ²¹ through their primary care provider (PCP). Their PCP can refer them to in-person or telephone counseling and can prescribe medications. This constitutes a scientifically and ethically appropriate standard against which to measure the experimental interventions.

2. Nicotine replacement therapy (NRT): Brief advice + 2 weeks of nicotine patches and/or lozenges mailed to subject

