NRT prescriptions will be entered into the EHR and signed by the study PI ([name]), printed and faxed to the MGH Outpatient pharmacy. The MGH Outpatient pharmacy will send the NRT by mail to the subject.

NRT will be distributed in a two-week allotment. The RC will screen participants for any self-reported contraindications to NRT use or other exclusion criteria before enrollment. High-risk comorbidities (e.g. cardiovascular disease, uncontrolled hypertension) will also be assessed but will not be grounds for withholding NRT since the risks of continued smoking outweigh the potential risks of using NRT in these conditions. After verbal consent, the PI will screen medical records of subjects randomized to NRT for contraindications or exclusion criteria prior to randomization. Participants will be instructed not to use the patch or lozenges while smoking, but rather to commence use when/if they make a quit attempt or practice quit attempt (lozenges only). The most common side effect of transdermal NRT is skin irritation. Other possible but rare side effects of all forms of NRT include cardiovascular (chest pain, hypertension, tachycardia, palpitations), metabolic (hot flashes, sweats), gastrointestinal (diarrhea, dyspepsia, nausea/vomiting, flatulence/gas, hiccups), musculoskeletal (arthralgia, myalgia), neurologic (headaches, dizziness), ophthalmic (lacrimation, nystagmus), respiratory (coughing), oropharyngeal (dry mouth, alteration of taste) and psychiatric (sleep disturbance, vivid dreams) manifestations.⁶² The most common side effects of nicotine lozenges include mouth irritation or ulcers, nausea, vomiting, hiccups, abdominal pain, diarrhea, headaches and palpitations. Randomized trials of combination nicotine replacement therapy have shown increased report of adverse events but not more serious adverse events or study withdrawal among subjects receiving combination therapy compared with subjects receiving NRT monotherapy. The risk of nicotine toxicity is rare in clinical trials. Among trial subjects who achieve higher cotinine levels with nicotine therapy than with smoking alone, the most common symptoms reported were nausea, vomiting, palpitations, dizziness, and headaches and all occurred in 0.5% or fewer trial subjects.⁶³

All study subjects will be asked about adverse reactions to the nicotine patch or lozenge at weeks 1, 2 and 6.

c. Devices

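### Sections IV.b and IV.c give opposite orders for the baseline survey and randomisation, so self-reported baseline data could be collected after allocation

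*Combined protocol and SAP*

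**What the plan says.** Four places in the protocol describe the steps between consent and allocation.

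- **Section III**, in the rationale for requiring a Partners PCP: "Patients undergo chart review by PI as part of eligibility screening for possible contraindications to NRT". The paragraph after the exclusion criteria repeats that the PI reviews the chart after verbal consent, and ends: "Subjects without contraindications will be randomized". It does not mention the baseline survey.
- **Section IV.b** (informed consent): "Following verbal informed consent, the PI will screen the medical chart of consented subjects for NRT contraindications or diagnoses in the exclusion criteria". It then says: "Subjects without contraindications will undergo baseline survey and then be randomized".
- **Section IV.c** (treatment assignment and randomisation) has a sentence fragment, "After verbal consent and chart review by the PCP", followed by: "Randomized enrollees will be asked to complete a baseline telephone survey".
- **Section V.b** (drugs used): "After verbal consent, the PI will screen medical records of subjects randomized to NRT for contraindications or exclusion criteria prior to randomization".

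Three other parts bear on the consequences. Section IV.a says that the enrolling research coordinator (RC) is not blinded, because that person registers text-messaging participants during the enrolment call. Section V.d lists the baseline interview items. Section VI (data analysis) compares EHR and interview baseline characteristics across the four groups, and moves from a chi-square test to logistic regression on any factor imbalanced at p<0.05.

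**The concern.** A baseline measurement is safe to use as a covariate because allocation cannot have influenced it. Section IV.c as worded removes that assurance. A participant who has just been assigned free medication or a text programme, or neither, may report different motivation, confidence or readiness as a result. An interviewer who knows the arm may also record answers differently.

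The analysis rule makes this worse. Section VI selects covariates because they differ between arms, so an item that allocation has shifted is more likely to be selected. If assignment to text messaging raised stated motivation, and motivation raises quit attempts, adjusting for motivation would remove part of the effect under test. Other patterns could bias the estimate in other ways, so the direction is not known in advance. The check on whether randomisation succeeded would also be misleading, because a difference caused by allocation would look like chance imbalance.

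In addition, anyone who drops out between randomisation and the survey has an allocation but no interview baseline. Section VI does not say how a missing baseline covariate would be handled in the adjusted model.

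**Working it through.** No arithmetic applies, because the point concerns the order of procedures. The statements compare as follows.

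| Section | Chart review | Baseline survey | Randomisation |
|---|---|---|---|
| III | By the PI, after consent | Not mentioned | After chart review |
| IV.b | By the PI, all consented subjects | Before randomisation | After the survey |
| IV.c | By the PCP | Asked of people already randomised | Before the survey |
| V.b | By the PI, of subjects allocated to NRT, but before randomisation | Not mentioned | After chart review |

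**Step 1: survey against randomisation.** Sections IV.b and IV.c are directly opposed. Section III is silent on the survey. The next paragraph of Section IV.c places text-messaging registration after the survey for those allocated to it, which fits either order. Section V.d places the interview at enrolment, which does not separate the two.

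**Step 2: does stratification settle it?** Section IV.c stratifies by practice and by readiness to quit in the next 30 days, so that answer must be known before allocation. This favours the Section IV.b order but does not prove it. The 30-day question could be asked at screening. The readiness item in the Section V.d interview cites the Contemplation Ladder, and the protocol does not say that the two are the same item.

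**Step 3: which data are exposed under the Section IV.c order?**
- Plausibly affected: motivation, confidence, perceived distress, interview-rated readiness and reported cigarettes per day.
- Little affected: race, ethnicity, education, years smoked and phone details.
- Not affected: age, sex, insurance, medical history and practice variables, which come from the EHR.

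**Step 4: which analyses use the exposed data?**
- The comparison of baseline characteristics across the four groups.
- The adjusted primary analysis, and the adjusted secondary analyses, if an exposed item is selected.
- The readiness-stratified analyses, but only if they use a readiness value recorded after allocation.
- Not the unadjusted chi-square test, which is the default for the primary outcome.

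**Step 5: chart review.** Section V.b cannot be carried out as written: nobody is allocated to NRT before randomisation. Sections III and IV.b, and the timing given in Section V.b itself, all put the PI review before allocation, so the restriction to NRT subjects reads as a slip. The PCP named in Section IV.c conflicts with the PI named in Sections III, IV.b and V.b, and stands in a broken sentence.

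**The case against.** The strongest reply is that Section IV.b is the only explicit step-by-step account, and that Section IV.c is visibly damaged text and weak evidence of a different intention. The damage is also bounded: covariates enter only after a significant imbalance, the primary outcome is a 12-week report of a quit attempt and not a change from baseline, and the protocol never says that participants learn their arm before the survey. All of this stands and limits the size of the point. It does not remove the contradiction. Both sentences are operative, and staff following Section IV.c would be complying with the protocol.

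Two stronger readings are tempting, and the documents support neither.

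- A reader might infer from Section V.b that eligibility screening applies to the NRT arms only, so that exclusions differ by arm and the factorial comparison fails. A review done before randomisation cannot depend on the arm, and Sections III and IV.b apply it without regard to arm. Section V.b also has the RC screen participants for contraindications and other exclusion criteria before enrolment, with no limit by arm. The protocol gives no chart-exclusion rate, so any figure for differential exclusion would be invented.
- A reader might infer that stratifying by readiness makes the Section IV.c order impossible. Step 2 shows why that does not follow.

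**Conclusion.** The protocol contradicts itself on whether the baseline survey comes before or after randomisation, and this should be corrected. The consequence is a possible bias in covariate-adjusted estimates and in the baseline balance check, confined to a handful of subjective interview items, with possible loss of participants between allocation and baseline. Its size cannot be calculated from the documents.

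The concern rests on three assumptions: that staff follow Section IV.c; that the participant, the interviewer or both know the allocation at the time of the survey; and that the unblinded enrolling RC conducts the baseline interview, which the protocol does not state outright. If the Section IV.b order was followed throughout, only a wording error remains. The chart-review conflicts in Sections IV.c and V.b are wording errors to be put right at the same time, and are not evidence of arm-specific screening.

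**What to change.** 1. State one sequence in Sections III, IV.b, IV.c and V.b: verbal consent, chart review of every consented subject, baseline survey completed, then stratified randomisation.
2. In Section IV.c, make eligible consented subjects, not randomised ones, the people who are asked to complete the survey.
3. State that the 30-day readiness stratifier is recorded before allocation, and that the readiness-stratified analyses use that value.
4. Reconcile the chart reviewer named in Section IV.c with the PI review in Sections III, IV.b and V.b, and remove the restriction to NRT subjects from Section V.b.
5. If enrolment has begun, compare survey entry times with the time of allocation and report which order was followed. Section IX.a says that REDCap activity is logged and traceable. Limit adjustment covariates to those recorded before allocation.

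Items 1 to 4 cost wording only, since they largely restate what Sections III and IV.b already say. Item 5 costs a check of existing logs and a short statement in the report.
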